This is a pilot, randomized, open label clinical trial looking at the effects of different formulations of combined oral contraceptive pills (OCP) provided in therapy following the diagnosis of PCOS. Participants will be randomized in a 1:1 ratio to receive either a 21 day active hormone/7 day placebo pill pack (cyclical OCP) or an 168 day active hormone pill pack (6 month continuous OCP) and monitored with blood work and physical exams over the course of 6 months. Both groups will receive the same combined OCP component, containing 30mcg of ethinyl estradiol and 3 mg of Drospirenone (Yasmin).

7.5 BACKGROUND AND SIGNIFICANCE: Briefly provide the background and significance of this study (e.g. why is this study needed) (space limit: one half page):

If this is a first in humans study, please summarize the safety data from the animal studies. For pediatric drug or device studies, please identify if this is the first study in pediatric populations.

Polycystic Ovary Syndrome (PCOS) is a complex endocrine disorder that affects 5-15% of women worldwide¹ and is associated with multiple comorbidities such as obesity, Type 2 Diabetes, infertility and cardiovascular events^{2,3}. In the US, it is the most common endocrine abnormality of reproductive-aged women³. While the underlying cause remains unclear, women with PCOS are often found to have anovulatory cycles (menstrual dysfunction), clinical or biochemical signs of hyperandrogenism (such as elevated Testosterone levels, or male pattern hair growth and acne), and/or excessive follicle counts on ultrasound of the ovaries. Based on the Rotterdam Criteria (established in 2003) two out of the three above criteria must be met to diagnose PCOS⁴. While other definitions exist, the Rotterdam Criteria is widely used as an established diagnostic tool.

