In a study by Legro et al (2008), healthy women with regular menses were followed over a period of 6 months on either a continuous (168 day active pill) or a cyclical (21 day active/7day placebo) OCP that contained 20 mcg of ethinyl estradiol and 1mg of Norethindrone acetate. Findings from this study showed no difference in overall bleeding between treatment arms but a significant decrease in moderate/heavy bleeding days in favor of the continuous regimen. Both OCP treatment arms showed significant estrogen and Testosterone suppression compared to baseline during the 3rd week of each monthly cycle. While sex hormones (estrogen and Testosterone) were not evaluated during the placebo week in the cyclical group, there was notable rebound ovarian function noted in the cyclical formulation resulting in breakthrough menstrual bleeding. While this study was specifically done on healthy women, only one study has looked at continuous versus cyclical OCPs in women with PCOS.

Ruchhoeft et al (1996) showed in a fairly small study, that women with PCOS placed on a continuous OCP regimen for 3 months had significantly reduced Testosterone levels compared to baseline than those who were on cyclical preparations. Similarly, there was also a persistent reduction in LH, FSH and estradiol levels in the continuous treatment group throughout therapy. Alternatively, the study showed that individuals treated with a cyclical OCP had a significant rebound rise in their Testosterone, LH, FSH, and estradiol levels during the placebo week compared to mid-pill pack. These findings confirmed that it only takes a week off pills to (placebo week in cyclical OCPs) to cause rebound pituitary and ovarian activation resulting in increased hyperandrogenism. While having rebound ovarian function is not a bad thing in the general population as it allows for withdrawal bleeding, in patients with PCOS who require continuous suppression of ovarian function and Testosterone production, this could be an unwanted side effect.

7.7 * TREATMENT PROTOCOL: Is this a treatment study, i.e. does this study intend to provide treatment to individuals with a medical or psychological condition: (REQUIRED)

Yes No

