7.18 SPECIMENS SENT OUTSIDE UCSF - IDENTIFIABILITY: Will direct identifiers be associated with specimens or shared with other researchers and/or outside entities:

Yes
 No
 N/A - Specimens will not be shared with others

7.19 * FUTURE SPECIMEN USE: Will any specimens or portions of specimens be retained after the study is over for possible use in future research studies: (REQUIRED)

Yes No

7.21 * CLINICAL FOLLOW-UP DATA: Will clinical follow-up data be linked to specimens (i.e., will medical record information continue to be abstracted after the specimen is collected): (REQUIRED)

Yes No

Provide duration of follow-up or 'indefinitely':

7.26 STATISTICAL METHODS: Briefly summarize the methods and types of analyses that will be performed:

The means and standard deviation will be calculated for each of the blood tests within each treatment group and compared at the different time points to baseline measures. Additionally we will likely use a two sample t-test to estimate the difference in the mean Testosterone levels between the two treatment groups over the 6 month period. Analysis of covariance models, adjusted for the baseline measurement, will also likely be used to compare the treatment groups for metabolic parameters. Chi-Square analyses will be used to compare the treatment groups for reported anxiety and depression as analyzed categorically.

7.27 REFERENCES: List only the 5-10 most relevant references (a separate bibliography can be attached for reference purposes if this study involves novel approaches, agents, or an emerging technology that the IRB may not be familiar with):

3. The Rotterdam ESHRE/ASRM-Sponsored PCOS Consensus Workshop Group 2004 Revised 2003 consensus on diagnostic criteria and long-term health risks related to polycystic ovary syndrome. *Fertil Steril* 81:19-25.

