9.0 Sample Size and Eligibility Criteria

9.1 ENROLLMENT TARGET: How many people will you enroll:

60

If there are multiple participant groups, indicate how many people will be in each group:

As this is a pilot study we expect to enroll 30 participants into the cyclical OCP group and another 30 participants into the continuous 6 month OCP group with a total of sample size of 60.

9.3 SAMPLE SIZE JUSTIFICATION: Explain how and why the number of people was chosen. For multi-site studies, this is referring to the number that will be enrolled across all sites:

Since this is a feasibility or pilot study we expect to enroll 30 patients in each treatment arm for a total of 60 participants. Typically 7-9 new patients are seen in the PCOS Multidisciplinary clinic each month, however, due to COVID-19 there were restrictions on the number of individuals seen down to roughly 5-6 new patients are seen in the PCOS Multidisciplinary clinic each month. Now, there are new patients seen each month again. Given the protracted recruitment, any patient on chart review presenting to the Center for Reproductive Health with a complaint of PCOS seeking treatment, will also be considered for the study. **Additionally, all patients who met PCOS criteria in the last 2-10 years and present for a PCOS reassessment will be eligible for enrollment.** Assuming 2-3 outpatients seen in Multidisciplinary clinic and an additional 2-3 outpatients seen at the Center for Reproductive Health will meet criteria to participate in the study and will consent each month, we expect to reach our goal of at least 60 study subjects within the next 6 months.

9.4 * PARTICIPANT AGE RANGE: Eligible age ranges: (REQUIRED)

- 0-6 years
- 7-12 years
- 13-17 years
- 18-64 years
- 65+

9.5 * STUDY POPULATIONS: Data will be collected from or about the following types of people (check all that apply): (REQUIRED)

- Inpatients
- Outpatients
- Family members or caregivers
- Providers
- People who have a condition but who are not being seen as patients
- Healthy volunteers
- Students
- Staff of UCSF or affiliated institutions
- None of the above

9.6 * SPECIAL SUBJECT GROUPS: Check the populations that may be enrolled: (REQUIRED)

- Children / Minors
- Subjects unable to consent for themselves
- Subjects unable to consent for themselves (emergency setting)
- Subjects with diminished capacity to consent
- Subjects unable to read, speak or understand English
- Pregnant women
- Fetuses
- Neonates
- Prisoners

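### Section 7.26 names no analysis scale for the hormone results; a log-scale analysis with geometric mean ratios would use 30 women per arm more efficiently if the values are right-skewed

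*Combined protocol and SAP*

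**What the plan says.** The statistical plan is the single paragraph in section 7.26. For the blood tests it states: "The means and standard deviation will be calculated for each of the blood tests", by treatment arm, with comparison to baseline at each time point. For the main hormone it states: "we will likely use a two sample t-test to estimate the difference in the mean Testosterone levels between the two treatment groups" over the 6 months. A third sentence reads: "Analysis of covariance models, adjusted for the baseline measurement, will also likely be used to compare the treatment groups for metabolic parameters". The section does not say which tests count as metabolic.

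It names no log transformation, geometric mean, rank method or check of distribution. It names no between-arm test for SHBG, LH, FSH, estradiol or the free androgen index, although Aim 2 in section 7.3 lists the free androgen index beside testosterone. Nothing in the document gives an assay limit or says how a result below one is recorded or analysed.

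On size, section 9.3 says "we expect to enroll 30 patients in each treatment arm for a total of 60 participants", justified as a pilot, with no alpha, power, effect size or SD. Section 7.4 says "Participants will be randomized in a 1:1 ratio" and describes the trial as open label.

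**The concern.** Concentrations cannot fall below zero and often have a long upper tail. When they do, a few high values inflate the SD and pull the arithmetic mean, and a t-test on raw values needs a larger effect to reach significance than the same test on logged values. With 30 women per arm there is little precision to give away. Aim 2 and the hypothesis in 7.2 both concern the between-arm contrast in testosterone, so the contrast matters even though Aim 1 is feasibility.

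The silence on low results is a lesser worry. Section 7.6 cites a small study of women with PCOS in which "there was also a persistent reduction in LH, FSH and estradiol levels in the continuous treatment group throughout therapy", with a placebo-week rebound on the cyclical regimen. Section 7.10 times the month 1 and month 3 draws so that cyclical women are on placebo pills and continuous women on active pills. If the LH, FSH or estradiol assays return results below their limit, these would be expected more often in the continuous arm. A handling rule chosen after the data are seen, in an open-label trial, could then move the estimate.

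**Working it through.** **The plan's own figure.** The only stated number is 30 + 30 = 60. It has no power inputs, so there is no power calculation to reproduce. Everything below is illustrative.

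**1. Efficiency of the raw-scale t-test**

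Inputs from the documents: 30 per arm (9.3) and 1:1 allocation (7.4). Assumed: two-sided alpha 0.05, log-normal values, the same log-scale SD (s) in both arms, and no dropout.

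The log-scale standardised effect for 80% power is, by the normal formula, (1.960 + 0.842) × √(2/30) = 0.723. By the exact t distribution with 58 degrees of freedom it is 0.736. The effect is held at 80% power on the log scale for every s, and simulated trials (20,000 or more per setting) give the power of the equal-variance t-test on raw values. The coefficient of variation is √(exp(s²) − 1).

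| Log-SD s | CV | Log-scale power | Raw-scale power | Loss (points) |
|---|---|---|---|---|
| 0.3 | 31% | 80% | 78% | 2 |
| 0.4 | 42% | 80% | 77% | 3 |
| 0.5 | 53% | 80% | 75% | 5 |
| 0.6 | 66% | 80% | 73% | 7 |
| 0.8 | 95% | 80% | 68% | 12 |
| 1.0 | 131% | 80% | 61% | 19 |

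With no true difference, the raw test rejects in about 4% to 5% of trials across this range. It does not produce excess false positives; the cost is power alone.

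**2. Results below an assay limit**

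All inputs are assumed: s = 0.8, true continuous/cyclical ratio 0.50, and a limit that 20% of cyclical values fall below. With the cyclical log-mean set to 0:

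- Limit: log L = 0.8 × (−0.842) = −0.673, so L = 0.510.
- Share below in the continuous arm: Φ((−0.673 + 0.693)/0.8) = Φ(0.025) = 51%.
- Contribution of detected values to the mean, exp(μ + s²/2) × Φ((μ + s² − log L)/s): cyclical 1.377 × Φ(1.642) = 1.308; continuous 0.689 × Φ(0.775) = 0.538.

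The apparent ratio of raw means then depends on the rule, against a true 0.50:

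- Zero: 0.538/1.308 = 0.41, contrast exaggerated.
- Half the limit: (0.538 + 0.51 × 0.255)/(1.308 + 0.20 × 0.255) = 0.49, nearly neutral.
- Full limit: (0.538 + 0.51 × 0.510)/(1.308 + 0.20 × 0.510) = 0.57, contrast shrunk.
- Dropped: (0.538/0.49)/(1.308/0.80) = 0.67, contrast shrunk most.

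Half the limit is not neutral everywhere. In a second simulated case, with s = 0.4 and 20% against 6% below the limit, the mean difference was off by +22% (zero), +8% (half), −5% (full limit) and −20% (dropped). Dropping cut raw t-test power from about 77% to 56%, while a rank test with all non-detects tied at the bottom kept about 78%.

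**The case against.** The strongest reply is that 7.26 answers a form that asks for a brief summary, in a pilot with no stated power target, so no promised power is lost. Means, SDs and differences in units are a legitimate estimand that clinicians read easily. The raw scale is inferred from silence, and the t-test is itself only described as likely. The document gives no skewness; at a log-SD of 0.3 to 0.5 the loss is only 2 to 5 points. All of this stands, and it is why the point is minor. It does not remove the case for naming the scale, because doing so costs almost nothing.

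Three stronger readings are tempting and unsupported:

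- A reader might infer that a t-test is planned for every hormone. Section 7.26 names it for testosterone only: "two sample t-test to estimate the difference in the mean Testosterone levels". Metabolic parameters get baseline-adjusted analysis of covariance, and LH, FSH, estradiol and SHBG have no named between-arm test.
- A reader might infer that any handling of undetectable results biases the regimen difference towards none. The direction depends on the rule: zero substitution exaggerates the contrast, and dropping or full-limit substitution shrinks it. The plan chooses no rule.
- A reader might carry the non-detect argument over to the testosterone t-test. The cited persistent suppression concerns LH, FSH and estradiol, and raised testosterone is one route to meeting the hyperandrogenism criterion in 9.7. Nothing in the documents shows that undetectable testosterone should be expected.

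**Conclusion.** The concern holds as a minor improvement. Read at face value, 7.26 analyses hormones on the raw scale. If values are right-skewed, that gives up about 2 to 5 points of power at a log-SD of 0.3 to 0.5, 7 points at 0.6, and 12 to 19 points at 0.8 to 1.0, against 80% on the log scale with 30 per arm. These figures rest on log-normal data, equal log-scale SDs and full follow-up, none of which the documents establish. A reader might conclude that the planned t-test is invalid; it is not, since its type I error stays at or below about 5%.

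The missing rule for results below an assay limit is a gap in detail, not a wrong method. It is most relevant to LH, FSH and estradiol. Its size cannot be judged without assay limits, and its direction is open until a rule is chosen.

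**What to change.** In section 7.26:

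1. State that testosterone and the free androgen index, and also SHBG, LH, FSH, estradiol and insulin, are analysed on the log scale. Preferably use a model adjusted for the log of the baseline value, since section 7.10 already collects baseline testosterone, SHBG, LH, FSH, estradiol and insulin.
2. Report geometric means by arm and the continuous/cyclical ratio with a 95% confidence interval.
3. As a secondary item, fix one rule for results below the assay limit before analysis, either a censored-data model or a rank-based method, and report the proportion undetectable by arm. The censored model leans on the log-normal shape; the rank method does not, but gives no ratio estimate by itself. Sections 6.3 and 7.16 show that more than one laboratory is used, so each should return its numeric limit with any such result.

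The cost is a few sentences and a standard model, with no added visit, sample or participant. The one downside is that results read as ratios instead of differences in units; raw means and SDs can still be tabulated alongside.

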7.0 Research Plan and Procedures

7.1 This new consolidated section requests information about:

- Hypothesis
- Aims
- Study Design
- Background and Significance
- Preliminary Studies
- Procedures
- Statistical Methods
- References

Later sections include:

- Drugs and Devices
- Sample Size, Eligibility, and Subjects
- Recruitment and Consent
- Risks and Benefits
- Data and Safety Monitoring Plan
- Confidentiality, Privacy and Security
- Financial Considerations
- Qualifications of Personnel
- Other Approval and Registrations

7.2 HYPOTHESIS: Describe the hypothesis or what the study hopes to prove **(Help Text updated 9/13):**

We propose that patients with Polycystic Ovary Syndrome (PCOS) on a continuous 6 month active oral contraceptive (OCP) preparation (no placebo pills for 6 months straight) will have improved Testosterone suppression as compared to patients taking cyclical (monthly) OCPs, who may have rebound ovarian function during days 21-28 of their menstrual cycle when receiving sugar pills. With continuous OCP use we also hypothesize that patients will have improved clinical findings of hyperandrogenism (acne and hirsutism) compared to cyclic OCP users.

7.3 AIMS: List the specific aims:

1. To conduct a pilot feasibility study observing the use of 2 formulations of an OCP (continuous 168 day active hormone pills vs. cyclical 21 day active/7day placebo pill packs) in patients with Polycystic Ovary Syndrome (PCOS).
2. To determine the effect of 6 months of continuous (168 days of active hormone pills) vs. cyclical (21 day active and 7 day placebo pills) OCP therapy on biochemical findings of hyperandrogenism (Testosterone levels and free androgen index).
3. To determine the effect of 6 months of continuous (168 days of active hormone pills) vs. cyclical (21 day active/7 day placebo pills) OCP therapy on cutaneous findings of hyperandrogenism (male pattern hair growth also known as hirsutism and acne).
4. To determine the effect of 6 months of continuous (168 days of active hormone pills) vs. cyclical (21 day active/7 day placebo pills) OCP therapy on self reported symptoms of anxiety and /or depression as collected from validated questionnaires.

7.4 DESIGN: Briefly describe the study design (e.g., observational, interventional, randomized, placebo-controlled, blinded, cross-over, cross-sectional, longitudinal, pharmacokinetic, etc.):

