All potential participants in the study that go through the PCOS Multidisciplinary clinic have routine baseline blood work done (at least 1 month off any oral contraceptive pill) which includes total and free Testosterone levels, sex hormone binding globulin (SHBG), estradiol, luteinizing hormone (LH), follicle stimulating hormone (FSH), Hemoglobin A1c (HbA1c), insulin, fasting glucose, and a lipid panel. If baseline blood work is done > 2 months prior to enrollment, we will repeat these levels to ensure accuracy prior to start of study. As part of the clinic visit, patients routinely fill out a lengthy survey which includes a quality of life assessment and self-assessments regarding acne and hair growth. Potential participants will also have a routine initial dermatological exam to evaluate for hirsutism (using the modified Ferriman Gallwey aka mFG

score) and acne which takes place on their initial visit to clinic, prior to enrollment in the study. This information will all be included in the information gathered about each participant who enrolls in the study as it will provide baseline values.

All potential participants that present to the clinic for a reassessment will fill out a lengthy survey which includes a quality of life assessment and self-assessments regarding acne and hair growth. Potential participants will also have a routine initial dermatological exam to evaluate for hirsutism (using the modified Ferriman Gallwey aka mFG score) and acne which takes place on their initial visit to clinic, prior to enrollment in the study. This information will all be included in the information gathered about each participant who enrolls in the study as it will provide baseline values. If the potential participant still meets criteria for PCOS and meets criteria for the CCOUP study (see below), they will have routine baseline blood work done as a part of the study which includes total and free Testosterone levels, sex hormone binding globulin (SHBG), estradiol, luteinizing hormone (LH), follicle stimulating hormone (FSH), Hemoglobin A1c (HbA1c), insulin, fasting glucose, and a lipid panel.

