Those who meet criteria to take part in the study (women between the ages of 15-40 years, diagnosed with PCOS and have findings of hyperandrogenism either by serum Testosterone levels above the normal reference range and/or by their mFG score ($>/=5$), are recommended to start an oral contraceptive pill for therapy), and give consent, will be randomized into either of two oral contraceptive (OCP) treatment groups. The two treatment groups consist of either 1. Ethynodiol diacetate 30mcg-Drospirenone 3 mg: 21 day active/7day placebo pill pack or 2. Ethynodiol diacetate 30 mcg-Drospirenone 3 mg:168 day active hormone pills. While this study involves an intervention, it is important to address that the hormonal contraceptive therapy being administered is routinely used in the care of women diagnosed with PCOS who are not acutely interested in fertility. Instructions will be given to participants in the continuous treatment arm to remove all placebo/sugar pills from each OCP pack so that they continuously take active hormone pills throughout the study time frame.

Study subjects will be expected to take their OCP pills at the same time each day for the length of the study (6 months). On the 4th, 12th and 24th week of therapy (roughly the 1st, 3rd and 6th month), repeat blood work will be drawn and is detailed below.

At 1 month into therapy, (near the end of the 4th week on either OCP regimen) both treatment groups will be expected to come into the clinic for blood work (total Testosterone, SHBG, estradiol, LH, and FSH levels will be checked). As this is not considered routine labs, the study will cover the cost so that participants are not charged. At the time of the blood draw, subjects in the cyclical group should be on placebo/sugar pills and those in the continuous group on active hormone pills.

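### The between-arm testosterone test in 7.26 ignores a baseline value that is already collected, while baseline-adjusted ANCOVA is kept for metabolic parameters that no aim names

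*Combined protocol and SAP*

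**What the plan says.** The lead hypothesis in 7.2 is that women on the continuous regimen "will have improved Testosterone suppression as compared to patients taking cyclical (monthly) OCPs". Aim 2 in 7.3 is the effect of the two regimens on "biochemical findings of hyperandrogenism (Testosterone levels and free androgen index"). The other aims are feasibility, hirsutism and acne, and anxiety or depression.

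Section 7.26 uses baseline in two places and leaves it out in a third:

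- **Within arms.** Means and standard deviations are calculated "for each of the blood tests within each treatment group and compared at the different time points to baseline measures".
- **Between arms, testosterone.** "we will likely use a two sample t-test to estimate the difference in the mean Testosterone levels". The sentence refers to the six-month window. It names no covariate, visit or per-patient summary.
- **Between arms, other outcomes.** "Analysis of covariance models, adjusted for the baseline measurement, will also likely be used to compare the treatment groups for metabolic parameters".

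No between-arm method is given for free androgen index. Follow-up blood is drawn "On the 4th, 12th and 24th week of therapy" (7.10). New clinic patients have baseline blood work "at least 1 month off any oral contraceptive pill". On sample size, 9.3 says "Since this is a feasibility or pilot study we expect to enroll 30 patients in each treatment arm" and gives no power, effect size or standard deviation.

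**The concern.** The better between-arm method in 7.26 goes to outcomes outside the aims, and the outcome at the head of the hypothesis gets the less precise one. The within-arm comparison with baseline does not repair this, because it does not adjust the difference between arms.

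What is at stake is the width of the testosterone interval. A pilot with 30 per arm and no power claim will be judged, for this outcome, on how well it estimates the difference for a later trial. If a woman's baseline testosterone predicts her on-treatment value at all, leaving it out carries avoidable between-woman variation into the estimate.

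**Working it through.** **Inputs.** n = 30 per arm is from 9.1 and 9.3. Three post-baseline draws are from 7.10. The documents give no testosterone SD and no correlations, so results are in SD units of a single follow-up value. The following are assumed: baseline correlation r with each follow-up visit, between-visit correlation w of 0.5 to 0.7, equal SD at all visits, and all 60 women analysed. The plan states no precision or power figure, so there is nothing of its own to reproduce.

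**Formulas.** Half-width of the 95% interval = t × m × sqrt(2/30), with sqrt(2/30) = 0.2582. The critical value t is 2.0017 unadjusted (58 df) and 2.0025 adjusted (57 df). The multiplier m is:

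- single visit: 1 unadjusted, sqrt(1 − r²) adjusted;
- three-visit mean: sqrt(v) unadjusted, sqrt(v − r²) adjusted, where v = (1 + 2w)/3. This gives v = 0.667 at w = 0.5 and v = 0.800 at w = 0.7.

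**Results at r = 0.3.**

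| Summary | Unadjusted | Adjusted |
|---|---|---|
| Single visit | 2.0017 × 1 × 0.2582 = 0.517 | 2.0025 × sqrt(0.91) × 0.2582 = 0.493 |
| Three-visit mean, w = 0.5 | 2.0017 × sqrt(0.667) × 0.2582 = 0.422 | 2.0025 × sqrt(0.577) × 0.2582 = 0.393 |
| Three-visit mean, w = 0.7 | 2.0017 × sqrt(0.800) × 0.2582 = 0.462 | 2.0025 × sqrt(0.710) × 0.2582 = 0.436 |

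**Cost of estimating the slope.** On average over randomisations the adjusted SE is multiplied by sqrt(1 + 1/56) = 1.009. The adjusted column then becomes 0.498, 0.396 and 0.440, each still below its unadjusted counterpart.

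**In women.** For the three-visit mean the equivalent unadjusted size per arm is 30v/(v − r²): 20/0.577 = 34.7 and 24/0.710 = 33.8. Dividing by 1 + 1/56 gives 34.1 and 33.2, a gain of about 3 to 4 women per arm.

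**If baseline is uninformative (r = 0), single visit.** 2.0025 × 1.009 × 0.2582 = 0.522 against 0.517, about 1% wider on average. In one trial with a chance baseline imbalance of 2 standard errors, the SE is multiplied by 1/sqrt(1 − 4/62) = 1.034, about 3.4% wider. Dropout would raise these costs slightly. Break-even r is about 0.14 for a single visit and 0.11 to 0.12 for the mean.

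**Higher correlations.** For a single visit, r = 0.5 gives 0.448 and r = 0.7 gives 0.369. These rows are the least likely here. Baseline is measured off OCP and follow-up on it. The timeline footnotes in 7.10 also imply that the baseline laboratory differs between women: returning patients, and those whose screening bloods are more than two months old, have baseline testosterone sent to the central laboratory, while the others keep an outside-laboratory value.

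**Are the three draws comparable?** For months 1 and 3, 7.10 says the cyclical arm should be on placebo pills at the draw. The month-6 paragraph is silent. By count, the placebo days of a 28-day pack are days 22-28, so week 4 is days 22-28, week 12 is days 78-84, and week 24 is days 162-168, the end of the sixth pack. The draws align if the week-24 timing is kept, but the month-6 text does not say so.

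**The case against.** The strongest reply is that an unadjusted t-test in a randomised pilot is valid, that 7.26 answers a form asking for a brief summary, and that both methods are marked as likely, so ANCOVA for testosterone is not ruled out. All of that is true. But the plan does not assign ANCOVA to testosterone. Testosterone has its own sentence and its own test, and 7.10 lists lipids, glucose, insulin and HbA1c apart from the sex hormones at month 3. Reading metabolic parameters to include testosterone would stretch the text.

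The second reply is that the gain is assumed and may be small. This stands in part. At r = 0.3 the saving is about 0.02 to 0.03 SD, and the off-treatment, mixed-laboratory baseline argues against counting on more. The case rests on asymmetry: the average cost is about 1%, the break-even correlation is low, and the change takes a few sentences.

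The third reply is that averaging visits could mix pill phases. The week count mostly answers it, although the month-6 wording needs to be reconciled with months 1 and 3.

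A reader might also infer that the t-test is biased, that 60 women is the wrong number, or that 1% is the most that adjustment can cost. The documents support none of these. Randomisation protects the t-test. Section 9.3 makes no statistical claim that could be contradicted. The 1% is an average with everyone analysed, not a ceiling. Nor is the missing visit or summary a fault of its own: in a brief methods statement it is missing detail, best settled in the same edit.

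**Conclusion.** The point holds as one of precision, not validity. Section 7.26 leaves the between-arm testosterone comparison unadjusted and keeps the baseline-adjusted model for outcomes that no aim names, although baseline testosterone is already collected. At 30 per arm and an assumed baseline correlation of 0.3, the half-width falls from 0.52 to 0.49 SD (single visit) or from 0.42-0.46 to 0.39-0.44 SD (three-visit mean, between-visit correlation 0.5 to 0.7). Larger gains need higher correlations, which are less likely here. All sizes rest on assumed correlations, equal SDs and no dropout. The change should be made because it is cheap and concerns the lead outcome; the trial is sound without it.

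**What to change.** In 7.26, replace the testosterone t-test with the ANCOVA already planned, adjusted for the baseline value, and apply it to both testosterone and free androgen index. Name the mean of weeks 4, 12 and 24 as the primary summary, which fits the six-month window in the current sentence. Report the adjusted difference with its 95% confidence interval and keep per-visit differences secondary. Add an indicator for baseline laboratory (outside or central) as a sensitivity analysis. In 7.10, reconcile the month-6 paragraph with those for months 1 and 3 on pill phase at the draw, so that the three values averaged are comparable.

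Cost: a few sentences and a few lines of code, with no new visits, blood draws or data. Apart from the small loss of precision if baseline proves uninformative, the downside is that a visit mean dilutes an effect that appears only late. The secondary per-visit differences would show such an effect.
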